## 8. Objective

### 8.1. PRIMARY ENDPOINT – ARM A (TOTAL SHOULDER ARTHROPLASTY / HEMIARTHROPLASTY (TSA/HA))

**Degenerative, rheumatoid or post-traumatic arthritis of the shoulder joint and proximal humerus fractures:**

The primary objective of the clinical investigation is to demonstrate non-inferiority of the ASES Shoulder Score at 24 months postoperative compared to the benchmark literature for Arm A. The 24 months mean ASES Shoulder Score result of the RFX System (TSA/HA) will be compared to the pooled postoperative mean estimate of the control group (58.74 points). The pooled standard deviation of the postoperative ASES Shoulder Score result of the benchmark (20.33 points) was used to determine lower limit. The lower maximum acceptable difference ( $-\theta$ ) is 38.41 points (mean of control -  $\theta$  or  $58.74 - 20.33 = 38.41$  points).

Based on the underlying distribution of the data and the result of the normality assessment, either the parametric one-sample t-test or the non-parametric one-sample sign test will be used to compare the 24 months postoperative ASES Shoulder Score results of the ReUnion RFX System (TSA/HA) against the value of 38.41 points.

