Path	Non-inferiority – ReUnion RFX Arm A (TSA/HA) (A) $\geq$ Benchmark (B, explorative analysis in this document)					
Hypotheses Pair	Null ( $H_0$ )		A – B $< -\theta$			
	Alternative ( $H_1$ )		A – B $\geq -\theta$			
Benchmark Timepoint	24 months postoperative					
Benchmark no. of sources	5					
Benchmark Mean	58.74 (pooled mean ASES [points])					
Benchmark Std. Dev.	20.33 (pooled std. dev. ASES [points])					
Benchmark Value	Pooled mean ASES minus pooled std. dev. ASES					
Non-Inferiority Margin (- $\theta$ )	$58.74 - 20.33 = 38.41$ points					
Software Used	IBM SPSS Sample Power V3.0					
IBM SPSS Sample Power Output						
One goal of the proposed clinical investigation is to test the null hypothesis that the population mean is 58.74 points. The criterion for significance (alpha) has been set at 0.05. The test is 2-tailed, which means that effects in both directions will be interpreted. With the proposed sample size of 10 cases, the clinical investigation will have power of 80.3% to yield a statistically significant result. This computation assumes that the population from which the sample will be drawn has a mean of 58.74 points with a standard deviation of 20.33 points. The observed value will be tested against a theoretical value (constant, non-inferiority margin) of 38.41 points.						

[figure not shown]
Estimated overall drop-out rate is 56% which leads to the requirement of enrolling an additional 6 subjects into the clinical investigation.

Sample Size	Overall number of subjects to be enrolled: 16 subjects (rounded up to 20 subjects)
Overall Sample Size (multiplied by number of indications = 5)	100 subjects

Table 2a: Sample Size Justification Arm A (TSA/HA)

[figure not shown]

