## 11.3. ANALYSIS AND EVALUATION

### 11.3.1. Statistical Analysis

Evaluation elements are defined as the questions on the CRF/eCRF. The SAP lists all evaluation elements and secondary elements which will be based on calculations between two or more evaluation elements.

All quantitative variables, including those based on calculations (secondary elements), will be analyzed with a case summary evaluation before the detailed characteristics and parameters can be evaluated. A case summary contains a listing of the number of valid cases/values, missing cases/values (if any) and total cases/values in the specific analysis. In general, as central position parameter for quantitative variables the mean, median and mode will be analyzed. As variation parameter the standard deviation, 95% confidence interval of the mean, interquartile range and range (based on maximum and minimum) will be calculated. All quantitative variables will be assessed for normality using the Shapiro-Wilk test. For optional visualization of quantitative variables, box-and-whisker plots will be used. Additional analyses like skewness and kurtosis measures or standard errors are optional also.

All qualitative variables, including those based on summaries (secondary elements), will be analyzed listing the proportions, frequencies, column and row totals, and missing proportion, if any.

The SAP reflects this approach and specifies the variables characteristics (quantitative or qualitative) in detail together with the related analysis strategy. This also includes calculation and summaries based on primary elements and the required analysis.

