### 11.3.2. Primary Analysis / Endpoint

The objective of the clinical investigation is to demonstrate the non-inferiority (equal or better) of the ASES Shoulder Score in relationship to the officially cleared indications in comparison to respective clinical outcome data in the scientific literature.

Data collection of ASES Shoulder Score will be collected according to the schedule in Table 1, Schedule of Events. This will be repeated annually in all subjects who have the prosthesis with full or partial implant survival (including all subjects without removal of all endo-prosthesis components).

The 24 months postoperative results for subjects implanted with ReUnion RFX System will be compared to a historical group and results reported by respective clinical outcome data in the scientific literature.

[figure not shown]
Higher ASES Shoulder Score results are linked to better subject results and vice versa.

The clinical investigation endpoint is non-inferiority to the control, meaning the clinical investigation result should be equal or better than the control. In this clinical investigation, an equal or better ASES Shoulder Score result means equal or more ( $\geq$ ). As only results from samples will be captured, results are mostly estimates of the true population parameter. These

estimates vary by a certain area, where it is expected that the true population parameter falls within. Based on this, it is required to specify a lower limit for the acceptable difference or zone of indifference, denoted as  $-\theta$ .

Hypotheses are developed to allow for a comparison of the 24 months postoperative ASES Shoulder Score effectiveness/performance between the two underlying populations. The 24 months post-operative ASES Shoulder Score is the primary endpoint of this clinical investigation. Hypothesis tests will be one-sided with a significance level  $\alpha$  of 5%.

[figure not shown]
Table 3a: Arm A (TSA/HA)

Hypothesis	Equations	Interpretation
Null ( $H_0$ )	$A - B < -\theta$	Central tendency of A is inferior to the central tendency of B.
	ReUnion RFX System (TSA/HA) – Control (Benchmark) $< -\theta$	
Alternative ( $H_1$ )	$A - B \geq -\theta$	Central tendency of A is non-inferior to the central tendency of B.
	ReUnion RFX System (TSA/HA) – Control (Benchmark) $\geq -\theta$	
		
Possible Evidence (p)	Possible Decisions	Possible Conclusions – ASES score

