p-value $> \alpha$ (0.05)	Fail to reject null hypothesis ( $H_0$ )	ReUnion RFX System (TSA/HA) $<$ Control (Benchmark) Insufficient evidence to reject the null hypothesis ( $H_0: A - B < -\theta$ ) at the pre-determined significance level of 5%.
p-value $\leq \alpha$ (0.05)	Reject null hypothesis ( $H_1$ )	ReUnion RFX System (TSA/HA) $\geq$ Control (Benchmark) Sufficient evidence to reject the null hypothesis ( $H_0: A - B < -\theta$ ) at the pre-determined significance level of 5%.

The primary objective of the clinical investigation is to demonstrate non-inferiority of the ASES Shoulder Score at 24 months post-operative compared to the benchmark literature for Arm A. The 24 months mean ASES Shoulder Score result of the RFX System (TSA/HA) will be compared to the pooled postoperative mean estimate of the control group (58.74 points). The pooled standard deviation of the post-operative ASES Shoulder Score result of the benchmark (20.33 points) was used to determine lower limit. The lower maximum acceptable difference ( $-\theta$ ) is 38.41 points (mean of control -  $\theta$  or  $58.74 - 20.33 = 38.41$  points).

Based on the underlying distribution of the data and the result of the normality assessment, either the parametric one-sample t-test or the non-parametric one-sample sign test will be used to compare the 24 months postoperative ASES Shoulder Score results of the ReUnion RFX System (RSA) against the value of 38.41 points.

Table 4a: Arm B (RSA)

Hypothesis	Equations	Interpretation
Null ( $H_0$ )	$A - B < -\theta$	Central tendency of A is inferior to the central tendency of B.
	ReUnion RFX System (RSA) – Control (Benchmark) $< -\theta$	
Alternative ( $H_1$ )	$A - B \geq -\theta$	Central tendency of A is non-inferior to the central tendency of B.
	ReUnion RFX System (RSA) – Control (Benchmark) $\geq -\theta$	
		
Possible Evidence (p)	Possible Decisions	Possible Conclusions – ASES score
p-value $> \alpha$ (0.05)	Fail to reject null hypothesis ( $H_0$ )	ReUnion RFX System (RSA) $<$ Control (Benchmark) Insufficient evidence to reject the null hypothesis ( $H_0: A - B < -\theta$ ) at the pre-determined significance level of 5%.
p-value $\leq \alpha$ (0.05)	Reject null hypothesis ( $H_1$ )	ReUnion RFX System (RSA) $\geq$ Control (Benchmark) Sufficient evidence to reject the null hypothesis ( $H_0: A - B < -\theta$ ) at the pre-determined significance level of 5%.

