Benchmark Mean	74.48 (pooled mean ASES [points])	
Benchmark Std. Dev.	11.08 (pooled std. dev. ASES [points])	
Benchmark Value Non-Inferiority Margin (-θ)	Pooled mean ASES minus pooled std. dev. ASES 74.48 – 11.08 = 63.40 points	
Software Used	IBM SPSS Sample Power V3.0	
IBM SPSS Sample Power Output		

One goal of the proposed clinical investigation is to test the null hypothesis that the population mean is 74.48 points. The criterion for significance (alpha) has been set at 0.05. The test is 2-tailed, which means that effects in both directions will be interpreted. With the proposed sample size of 10 cases, the clinical investigation will have power of 80.3% to yield a statistically significant result. This computation assumes that the population from which the sample will be drawn has a mean of 74.48 points with a standard deviation of 11.08 points. The observed value will be tested against a theoretical value (constant, non-inferiority margin) of 63.40 points.
		
IBM SPSS Sample Power Output – Screenshot		

Estimated overall drop-out rate is 56% which leads to the requirement of enrolling an additional 6 subjects into the clinical investigation.
		
Sample Size	Overall number of subjects to be enrolled: 16 subjects (rounded up to 20 subjects)	
Overall Sample Size (multiplied by number of indications = 5)	100 subjects	

Table 3.2.2: Sample Size Justification Arm B (RSA)

In conclusion, the calculated number of subjects to be enrolled (10) plus the estimated overall drop-out rate of 56% predicts enrollment of 16 subjects (rounded up to 20) per indication. Since the five cleared indications and the proposed sample sizes are identical for the two clinical investigation arms, the sample size of one indication (n=20) will be multiplied by five to reflect the underlying subject population adequately. As a result, an enrollment target of 100 subjects in total will be aspired (ideally, but not necessarily, composed with 20 subjects per indication).

4. Methods

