4.7. CONFIDENCE INTERVALS AND P-VALUES

The following acceptance / rejection criteria were used for this clinical investigation:

Parameter	Acceptance / rejection criteria
Confidence level (1- α)	0.95 (95%)
Significance level (α)	0.05 (5%)
Power (1- β)	0.80 (80%)
Beta-level (β)	0.20 (20%)
Confidence interval of mean	95%
p-value indicating significance	≤ 0.05

Table 4.7: Acceptance / Rejection Criteria

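### The stated 80.3% power is for a 2-tailed 5% t-test, but the decision rule is one-sided at 5% (89.8% at the same n), and the tested parameter is not named (minor)

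*Protocol*

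**What the plan says.** **Planning.** The sample-size tables in both documents set alpha 0.05, power 0.80 and Tails = 2. Of the Arm A calculation the protocol says "The test is 2-tailed, which means that effects in both directions will be interpreted". All four tables give the same result, here from SAP 3.2.2: "With the proposed sample size of 10 cases, the clinical investigation will have power of 80.3% to yield a statistically significant result". The text around it places the null at a population mean of 58.74 (Arm A) or 74.48 (Arm B), although the value tested against is 38.41 or 63.40.

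**Decision rule.** Protocol 11.3.2 and SAP 3.1.1: "Hypothesis tests will be one-sided with a significance level" of 5%.

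**General criteria.** Protocol section 11 and SAP Table 4.7 (row "p-value indicating significance") give 0.05 without saying one- or two-sided.

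**Parameter.** The objective is about the 24-month mean, which "will be compared to the pooled postoperative mean estimate of the control group". The hypothesis tables say only "Central tendency of A is non-inferior to the central tendency of B". Depending on the normality assessment, "either the parametric one-sample t-test or the non-parametric one-sample sign test will be used". SAP 4.10 requires a non-parametric method when normality fails and rules out transformation.

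**The concern.** A power figure should describe the test that decides success. Here the planning text and the decision rule describe two different tests of the primary endpoint, and the general criteria do not settle which applies. One implies a 2.5% chance of a false non-inferiority claim at the limit, the other 5%, and each needs a different observed mean for success. The study is unblinded with no concurrent control, so this should be fixed before the 24-month scores are analysed.

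The second issue is what is being tested. A t-test against a constant concerns the mean; a sign test concerns the median. Both limits are a mean minus an SD. Because the hypothesis tables do not name the parameter, the data decide which one a claim of non-inferiority refers to, and the two arms could end up with different ones.

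**Working it through.** **Inputs (protocol 11.1.1 and 11.1.2).** Arm A: mean 58.74, SD 20.33, limit 38.41. Arm B: mean 74.48, SD 11.08, limit 63.40. The standardized effect is d = (58.74 − 38.41)/20.33 = (74.48 − 63.40)/11.08 = 1.00 in both arms.

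**1. The plan's figure.** One-sample t-test, n = 10, df = 9, noncentrality d√n = √10 = 3.162. Two-sided 5% (critical t 2.262): power 80.3%, which reproduces the plan. One-sided 2.5% also gives 80.3%, because the opposite tail contributes almost nothing.

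**2. The test in the decision rule.** One-sided 5% (critical t 1.833), same inputs: power **89.8%**. It is 75.4% at n = 7 and 81.5% at n = 8, so 80% is already reached at n = 8.

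**3. What the level changes.** Observed mean needed = limit + t × SD/√n, at the planned SDs:

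| Arm | n analysed | one-sided 5% | one-sided 2.5% |
|---|---|---|---|
| A | 10 | 50.2 | 53.0 |
| A | 22 | 45.9 | 47.4 |
| B | 10 | 69.8 | 71.3 |
| B | 22 | 67.5 | 68.3 |

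Example, Arm A with n = 22: 38.41 + 1.721 × 20.33/√22 = 45.9, against 38.41 + 2.080 × 20.33/√22 = 47.4.

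The 22 is illustrative: 100 × (1 − 0.56)/2 = 22. It assumes an equal split between arms, which the plan does not fix. It also applies at 24 months a drop-out rate that the plan cites to a follow-up of at least 10 years.

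**4. What n = 10 refers to.** Protocol 11.1.2 and SAP 3.2.2 apply the figure per indication and multiply by five. The primary test is run per arm. So neither 80.3% nor 89.8% is the power of the arm-level analysis. At 22 per arm the one-sided 5% t-test would have 99.8%.

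**5. The switch to the sign test.** The documents give no score distribution and no threshold specific to the Shapiro-Wilk step. I assumed beta-shaped scores on 0–100 with the planned SDs and a 0.05 threshold, and simulated the whole rule (t-test, or exact sign test if normality is rejected, one-sided 5%):

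| | Arm A, n=10 | Arm A, n=22 | Arm B, n=10 | Arm B, n=22 |
|---|---|---|---|---|
| Power, rule as planned | about 86–87% | 99% | 84% | 99% |
| Power, t-test alone | 88% | 99.8% | 87% | 99.5% |
| False-claim rate, rule as planned | about 4% | about 4% | about 6% | about 6% |
| False-claim rate, t-test alone | about 4% | about 4% | about 6% | about 5.5% |

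Power is at the planned means; the false-claim rate is with the true mean at the limit. In that second case the median is 36.7 in Arm A (38.41 − 36.7 = about 1.7 below) and 63.9 in Arm B (63.9 − 63.40 = 0.5 above). At n = 22 and the planned means, the switch occurs in about 7% (Arm A) and 13% (Arm B) of samples.

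**The case against.** The strongest defence is that the mismatch does no harm to power. The plan asks for 80%, and the test it will run exceeds that. The t-test or sign-test rule is pre-specified consistently in both documents, mean and median are both reported routinely, and the arms have separate hypotheses that are never compared. All of this stands, and it is why the point is minor. It does not remove the contradiction about the level, which changes the observed mean needed for success.

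Three stronger readings are tempting, and the documents do not support them.

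- *The trial is underpowered because the sign test has only 51.3% power at n = 10.* That figure is arithmetically right (9 of 10 scores must exceed the limit), but it assumes normal scores in a branch entered only after normality is rejected. It also uses a per-indication n for a per-arm test. Under normal scores the whole rule has about 88.5% at n = 10. The sign test alone falls below 80% only for an arm with fewer than about 16 analysed. That is possible, since arm sizes are open, but no figure in the plan shows it is likely.
- *The switch must go in order to control error.* Under the assumed shapes it makes almost no difference; the t-test alone gains about 2 points of power at n = 10. The case for naming the mean is interpretive.
- *The study report will quote a wrong power.* The reporting sections do not say that power will be reported.

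It would also be wrong to assume that one-sided 5% was intended. The only calculation shown matches one-sided 2.5%, and the documents do not settle the matter.

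**Conclusion.** The point holds in limited form, and its severity is minor. The stated 80.3% belongs to a 2-tailed 5% (equivalently one-sided 2.5%) t-test. The decision rule as printed has 89.8% at the same n and effect. These figures are exact for normal scores with a 1 SD effect. The error is conservative for power and calls for no additional subjects. What remains open is the false-claim rate, 5% or 2.5%, and with it the success threshold.

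The unnamed parameter is a secondary matter of interpretation. Its small numerical effect rests on the assumed beta shape, the planned SDs and a 0.05 Shapiro-Wilk threshold.

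**What to change.** The sponsor first confirms the intended level and then makes every section agree.

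- **If one-sided 5%:** set Tails = 1 in the four tables, replace the 2-tailed sentence, state 89.8% at n = 10 and say that this n is per indication. Add to protocol section 11 and SAP Table 4.7 that the primary endpoint is tested one-sided at 0.05.
- **If one-sided 2.5%:** keep 80.3%, again marked as per indication. Change protocol 11.3.2 and SAP 3.1.1 so that success means the lower limit of the two-sided 95% CI of the mean lies above 38.41 (Arm A) or 63.40 (Arm B).

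In either case:

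- Restate the null in the power text against 38.41 or 63.40 instead of 58.74 or 74.48.
- Write *mean* in the hypothesis tables.
- In protocol 8.1, 8.2 and 11.3.2 and SAP 3.1.1 and 6.6, make the one-sample t-test primary in both arms whatever the Shapiro-Wilk result, with the sign test as a sensitivity analysis. Exempt the primary endpoint from SAP 4.10.

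**Cost.** Text amendments only; no extra subjects or visits, and the enrolment target stays. Correcting Tails leaves the printed success rule unchanged. The 2.5% option tightens it by the amounts in the threshold table. Dropping the switch changes a pre-specified analysis, so it must be amended before the 24-month scores are analysed. The t-test is slightly liberal in Arm B under the assumed shape (about 5.4–6.0% at a nominal 5%), much the same as the current rule.

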### 11.3.3. Secondary Endpoints

The incidence of device-related AEs and implant survivorship will be assessed up to ten years after the index procedure and monitored through collection and analyses. These analyses will be part of the annual and final reports.

Furthermore, time to (earliest) device-related AEs will be analyzed as well. For analysis of the time to the (earliest) device-related AEs as well as the time to secondary procedure (revision, removal, reoperation), the Kaplan-Meier method will be used. The time between surgery and the last available assessment will be used together with the time between date of surgery and the date of secondary procedure. Considered variables, the level of measurement and the planned analysis steps are listed in detail in the SAP.

### 11.3.4. Additional Analyses

Additional analyses are outlined in the subsequent sections. Analysis details (variables, level of measurement, planned steps) are listed in-depth in the SAP.

- **Mortality**

For analysis of the time to death or mortality, the Kaplan-Meier method will be used. The times between surgery and the last available assessment will be used together with the times between date of surgery and the date of death. This analysis will be part of the annual and final reports.

- **Total ASES Shoulder Score – Within subject changes by visit**

The within subject score changes of the ASES Shoulder Score from visit to visit will be analyzed to help identify the changes on the subject level. This analysis will be part of the annual and final reports.

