#### 10.4. SCHEDULE OF EVENTS

Assessment	Pre-Operative	Operative/ Discharge	6 Weeks a, b (+/- 2 weeks)	6 Months a, b (+/- 3 weeks)	12 Months a, b (+/- 4 weeks)	24 Months a, b (+/- 4 weeks)	Annually b (+/- 4 weeks)
Informed Consent	X						
Demographics & Medical History	X						
Inclusion/Exclusion	X						
Physical Exam	X		X c	X c	X c	X c	X c
Surgical Procedure		X					
ASES Shoulder Score	X		X d	X d	X d	X d	X d
Image Evaluation e, f	X	X	X	X	X	X	X
Subject Disposition g			X	X	X	X	X
	Device-Related AEs/Incidents & Reoperations will be collected throughout the course of the clinical investigation.						
	
 
a. Follow-up visit schedule to reflect Institution's Standard of Care practices
 
b. If the subject misses a visit and is outside of the visit window, then every effort should be made to collect data instead of noting visit as missed. Visit windows are calculated from index event, and not from previous visit.
 
c. Evaluation may be collected when subject presents in-clinic for study visit.
 
d. Evaluation can be collected via phone.
 
e. Radiograph collection should follow Institution's Standard of Care practices and no additional x-rays should be made for study purposes.
 
f. CT scans may be collected if part of Institution's Standard of Care practices.
 
g. Subject Disposition assessment will occur at any time point for subject withdrawal prior to the completion of the clinical investigation.
 
						

Table 1: Schedule of Events

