6.7.2. Mortality

For analysis of the time to death or mortality, the Kaplan-Meier method will be used. The times between surgery and the most recent or last available assessment per subject will be used together with the times between surgery and the date of death. This analysis is part of the final report.

Evaluation Variable / Question	Level of Measurement	Recode and Analysis Plan
All Assessments - Mortality		
Creation of variable Difference between Date of Surgery [dd.mm.yyyy] and Date of Death [dd.mm.yyyy] in days  (Variable(s): VISITDT; DOSEDD)	Quantitative, ratio	Case summary with number and percentage of valid cases/values, missing cases/values (if any) and total cases/values. Mean, median, interquartile range, maximum, minimum, standard deviation, 95% confidence interval for mean, Shapiro-Wilk Test.
Creation of variable Difference between Date of Surgery [dd.mm.yyyy]	Quantitative, ratio	N/A (Analyzed above), used for survivorship

and Date of “most recent” Visit [dd.mm.yyyy] in days (Variable(s): VISITDT)		
Create new variable “Grouping variable - Mortality” (Variable(s): PRIMRSN)	Qualitative, nominal	- censored = survivors - events = death
Create new variable “Combined Time - Mortality” (Variable(s): VISITDT; DOSEDD)	Quantitative, ratio	- Use time between surgery and most recent visit for surviving subjects - Use time between surgery and death for deceased subject
Use variables “Combined Time - Mortality” and “Grouping variable - Mortality”	Qualitative, nominal Quantitative, ratio	Case summary with number and percentage of valid cases/values, missing cases/values (if any) and total cases/values. Kaplan-Meier survival analysis: subject ID, time, status, cumulative proportion, Kaplan-Meier estimate, standard error of KM estimate, number of cumulative events, number of remaining cases, mean for survival time with 95% confidence interval, survival graph, hazard graph.

Table 6.7.2.: All Assessments – Mortality Tables List

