6.7.3. Reoperation Surgery

For analysis of the time to the reoperation, the Kaplan-Meier method will be used. The times between surgery and the most recent or last available assessment per subject will be used together with the times between surgery and the date of reoperation (earliest reoperation in case that one subject experienced more than one reoperation). This analysis is part of the final report.

Evaluation Variable / Question	Level of Measurement	Recode and Analysis Plan
Adverse Events / Reoperation Surgery		
Creation of variable Difference between Date of Surgery [dd.mm.yyyy] and Date of First Reoperation [dd.mm.yyyy] in days (Variable(s): VISITDT)	Quantitative, ratio	Case summary with number and percentage of valid cases/values, missing cases/values (if any) and total cases/values. Mean, median, interquartile range, maximum, minimum, standard deviation, 95% confidence interval for mean, Shapiro-Wilk Test.
Creation of variable Difference between Date of Surgery [dd.mm.yyyy] and Date of “most recent” Visit [dd.mm.yyyy] in days (Variable(s): VISITDT)	Quantitative, ratio	N/A (Analyzed above), used for survivorship
Create new variable “Grouping variable – First Reoperation” (Variable(s): VISITDT)	Qualitative, nominal	- censored = survivors - events = first (earliest) Reoperation
Create new variable “Combined Time – First Reoperation” (Variable(s): VISITDT)	Quantitative, ratio	- Use time between surgery and most recent visit for surviving subjects - Use time between surgery and first reoperation for subjects with reoperation(s)
Use variables “Combined Time – First Reoperation” and “Grouping variable – First Reoperation”	Qualitative, nominal Quantitative, ratio	Case summary with number and percentage of valid cases/values, missing cases/values (if any) and total cases/values. Kaplan-Meier survival analysis: subject ID, time, status, cumulative proportion, Kaplan-Meier estimate, standard error of KM estimate, number of cumulative events, number of remaining cases, mean for survival time with 95% confidence interval, survival graph, hazard graph.

Table 6.7.3: All Assessments – Revision Surgery Tables List

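### The Kaplan-Meier rule ends event-free time at the last visit but dates events exactly, so any annual curve overstates recent risk; the protocol and SAP disagree on whether annual curves are produced

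*Protocol*

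**What the plan says.** Protocol 11.3.4 defines the mortality curve this way: "The times between surgery and the last available assessment will be used together with the times between date of surgery" and the date of death. Protocol 11.3.3 uses the same construction for revision, removal and reoperation: "The time between surgery and the last available assessment will be used together with the time between date of surgery" and the date of that procedure.

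The SAP codes the rule as a combined time variable. For event-free subjects, Tables 6.7.2 and 6.7.3 say: "Use time between surgery and most recent visit for surviving subjects". For deaths, Table 6.7.2 says: "Use time between surgery and death for deceased subject". Table 6.7.3 likewise uses the date of the first reoperation, and Table 6.6.2 the onset of the first device-related adverse event. None of these places gives a data-cut date, a check of status at the cut, or a point at which the curve stops.

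Events can become known between visits. The Schedule of Events (Protocol 10.4) states: "Device-Related AEs/Incidents & Reoperations will be collected throughout the course of the clinical investigation". Its note g lets a withdrawal be recorded at any time, and death is a withdrawal reason in 9.3. Protocol 13.4 requires serious device effects and serious incidents to reach the sponsor within 48 hours.

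On timing, Protocol 11.3.4 says of the mortality curve: "This analysis will be part of the annual and final reports". Protocol 11.3.3 places adverse event incidence and implant survivorship in the annual and final reports. SAP 3.1.2, 3.1.3, 6.6, 6.7.2 and 6.7.3 place all the Kaplan-Meier analyses in the final report only.

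**The concern.** Kaplan-Meier estimation needs the end of observation to be unrelated to the outcome. Here it is not. Visits are 12 months apart after month 12. Take a subject last seen at month 24 whose follow-up has reached month 33 at the data cut. If that subject died or was reoperated at month 30, the event counts at month 30. If nothing happened, the subject leaves the risk set at month 24. The nine months since the last visit enter only in the first case.

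Two things follow. Risk is overstated over the latest visit interval or so. Beyond the latest visit reached by any event-free subject, the risk set contains only subjects with events, so the curve falls to 0% at the last of them.

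Device-related adverse events and implant survivorship are the secondary endpoints, and Protocol 13 says the study is run to meet European post-market requirements. An annual curve that ends at 0% because of one event would misstate the device's record.

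**Working it through.** The documents give no event rate, expected survival or Kaplan-Meier figure, so there is none to reproduce.

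**Inputs from the documents**
- Visits at 6 weeks, 6, 12 and 24 months, then yearly (Protocol 10.3).
- Enrolment over 20 months (Protocol 7).
- 100 subjects in two arms, split not stated.
- Drop-out of 56% (Protocol 11.1).

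**Assumptions**
- 50 subjects per curve and uniform enrolment.
- Constant hazard of 2% per year, with 4% or 5% as alternatives.
- Events known up to the data cut.
- No loss for the annual report. For the final report, 56% loss spread evenly over 10 years: −ln(0.44)/10 = 8.2% per year.

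**Step 1: follow-up counted at a month-36 report.** Actual follow-up F runs uniformly from 16 to 36 months, mean 26.0. The last visit is month 12 for F from 16 to 24 (8/20 = 40%) and month 24 for F from 24 to 36 (60%). Mean time counted: 0.4 × 12 + 0.6 × 24 = 19.2 months. 26.0/19.2 = 1.35, so a crude rate is about 35% too high.

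**Step 2: the 24-month estimate.** Everyone has reached the month-12 visit, so the first year is unbiased: cumulative hazard 0.02. In months 12 to 24, only 60% of subjects can be at risk if event-free. Events count from everyone with F beyond that time: a fraction of 1 up to month 16, falling to 0.6 at month 24, on average (4 × 1 + 8 × 0.8)/12 = 0.867. Apparent hazard: 0.02 × 0.867/0.6 = 0.0289. Estimate: 1 − exp(−0.0489) = 4.8%. True value: 1 − exp(−0.04) = 3.9%. Simulation gives 4.8% to 4.9%.

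**Step 3: the fall to 0%.** No event-free subject counts beyond month 24, so any known event after month 24 takes the curve to 0%. The chance per subject is 0.6 × e^(−0.04) × [1 − (1 − e^(−0.02))/0.02] = 0.00573. For 50 subjects: 1 − (1 − 0.00573)^50 = 25.0%. Simulation gives 24% to 26%. At 4% per year the formula gives 42%.

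**Step 4: the 36-month estimate.** The mean is about 0.25 × 100% + 0.75 × 4.9% = 28.7% (simulation 28% to 29%), against a true 1 − exp(−0.06) = 5.8%. The median is 6.0%. The mean is therefore high because of the runs that drop to 0%. At 4% per year the mean is 48%, the median 15% and the true value 11.3%.

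**Step 5: a year later.** At a month-48 report every subject has passed month 24, and the 24-month estimate is correct (3.9%). The distortion has moved to the new end of the curve.

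**Step 6: sensitivity.** With loss of 8.2% per year and visit windows, 36-month survival at a month-36 cut averages 79.8% against a true 94.2% (2% per year). For 20 to 100 subjects per curve, hazards of 2% and 5%, and cuts from month 18 to 90, the curve ends at 0% in 2% to 31% of runs.

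**Step 7: final report.** With 56% loss and 2% per year, the estimate near 10 years is 18.7% against 18.0%. Across 20 to 100 subjects and hazards of 2% and 5%, the excess is 0.5 to 1.8 points, with a 0% curve in at most 0.1% of runs.

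**Step 8: events found only at visits.** At a month-36 cut and 5% per year, 36-month survival averages 88.6% against a true 86.1%, so risk is not overstated.

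**Step 9: remedies, month-36 report at 2% per year.** Ending both events and event-free time at the last visit due gives a 24-month estimate of 4.0% (true 3.9%) and no 0% curves. Censoring at the data cut with status confirmed gives a 36-month estimate of 5.7% to 5.9% (true 5.8%).

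**The case against.** The strongest reply is that the annual curves may never be drawn. SAP version 2 (28MAY2021) is later than protocol version 2 (08Aug2019), and its revision history says it was changed to separate interim from final analyses. The protocol refers to the SAP for the detailed analysis steps. Only the mortality curve is expressly annual. In 11.3.3 the sentence on annual reports precedes the paragraph that introduces Kaplan-Meier, so it covers implant survivorship without clearly covering that curve. This stands in part. If the SAP governs, the remaining error is about 1 point. But the SAP does not say that it overrides the protocol, and Protocol 11.3.4 is unambiguous.

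Other parts also stand. These analyses carry no hypothesis or threshold, and the SAP has no stopping rules. The SAP output includes the number of remaining cases and the standard error, so an alert reader could see that a final drop rests on one subject. Many foreseeable events are radiographic and would be found at visits, where risk is not overstated. The sentence on continuous collection covers device-related events and reoperations, not deaths, although deaths can be recorded as withdrawals at any time.

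A reader might infer from the 28% mean that annual curves typically show about five times the true risk. They do not: the median is 6.0% against 5.8%, and about a quarter of trials drop to zero. A reader might also infer that censoring at the last known contact is enough. Without a status check at the data cut, that date is usually the last visit, which is the present rule.

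**Conclusion.** The rule is explicit in both documents and gives wrong results for events learned between visits. The direction and the possible fall to 0% follow from the rule itself. The size depends on assumed hazards, arm size, enrolment pattern and data-cut dates that the documents do not give. With 50 subjects, 2% per year and no loss, a month-36 report overstates the 24-month risk by about 1 point (4.8% to 4.9% against 3.9%) and ends at 0% in about a quarter of trials.

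The documents do not support a claim that every Kaplan-Meier curve, or every adverse event, is materially affected. Earlier parts of the curve recover as later visits accrue, the final report is off by only about 1 point, and the primary endpoint is untouched. The point should be corrected wherever annual curves are produced, and the conflict over report timing should be resolved in any case.

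**What to change.** In Protocol 11.3.3 and 11.3.4 and SAP Tables 6.6.2, 6.7.2 and 6.7.3, apply one cut-off per subject to both events and event-free time. Either of two forms works.

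1. **No new data.** End each subject's time at the last scheduled visit that has fallen due by the data cut, or the last one before withdrawal. Count only events up to that visit, show the curve only up to the latest such visit, and list later events separately. A subject withdrawn because of the event being analysed (death, device removal) should keep the visit dates that would have applied, so that the event enters once its interval has closed.
2. **With a status check.** Sites confirm each subject's status at a stated data cut, and event-free subjects are censored at that confirmed date.

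State in both documents, in the same words, which Kaplan-Meier curves go into the annual reports and which only into the final report.

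The text change is a few sentences. Under the first form, the newest events enter the curve up to a year later, but are listed meanwhile. Under the second, sites carry out a status check at each data cut, which is additional data collection.
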